IND	Investigational New Drug
kg	kilogram
MBq	megabecquerel
mCi	millicurie
mGy	milligray
MicroC ³	microfluidic-cis-co-culture
mL	milliliter
mmol	millimole
mRCC	Metastatic Renal Cell Carcinoma
PACS	Picture Archiving and Communication System
PET	Positron Emission Tomography
PI	Principal Investigator
PSMA	Prostate-specific membrane antigen
RCC	Renal Cell Carcinoma
REM	Roentgen Equivalent Mammal
RF	Radio frequency
RPF	Radiopharmaceutical Production Facility
SAE	Serious Adverse Event
UP	Unanticipated Problem
UW	University of Wisconsin
UWHC	University of Wisconsin Hospital and Clinics

STATEMENT OF COMPLIANCE

The signature below constitutes the approval of this protocol and the attachments, and provides the necessary assurances that this trial will be conducted according to all stipulations of the protocol, including all statements regarding confidentiality, and according to local legal and regulatory requirements and applicable US federal regulations and ICH guidelines.

I agree to ensure that all staff members involved in this study are informed about their obligations in meeting the above commitments.

Principal Investigator: [name]

Signed:

Date:

[name].
Department of Radiology, Nuclear Medicine Section
University of Wisconsin School of Medicine and Public Health
University of Wisconsin Carbone Comprehensive Cancer Center

PROTOCOL SUMMARY

Title	Functional Microscale Organotypic Assays to Predict Patient Response to Anti-Angiogenesis Therapies.
IND Sponsor-Investigator	[name]
Co-Investigators	[name] E. [name] [name]
Participating Site	University of Wisconsin-Madison
Patient Population	Patients diagnosed with metastatic clear cell RCC that are surgical candidates
Accrual Objective	This research will enroll 15 subjects
Study Design	Phase 2, single-center, open-label study
Study Duration	The estimated accrual period is over 3 years
Primary Objective	The primary objective of this research is to evaluate response to systemic therapy, including anti-angiogenesis and/or immune-based therapies, via ¹⁸ F-DCFPyL PSMA-based PET/CT in patients with metastatic renal cell carcinoma and to compare qualitatively with conventional imaging response criteria (RECIST 1.1) and histopathological endpoints including isolation, enumeration and staining of Circulating Tumor Cells (CTC).
Secondary Objectives	1. Measure therapy response of patient specific uVESSEL model 2. Evaluate the predictive power and validate the uVESSEL model
Inclusion Criteria	
 Patients diagnosed with locally advanced (\geqcT3) or metastatic clear cell RCC, as proven by biopsy. Adults, 18 years of age or older. Surgical candidates who have clinical indication for nephrectomy and standard of care biopsy of metastatic disease followed by possible standard of care systemic anti-angiogenesis based treatment regimen Have consented to participate in the UWCCC Biobank.
Exclusion Criteria	
 Patients who have received prior RCC systemic therapies Prior history of prostate cancer Prior history of any other malignancy within the last 2 years, other than skin basal cell or cutaneous superficial squamous cell carcinoma that has not metastasized and superficial bladder cancer Unable to lie flat during or tolerate PET/CT Serum creatinine $>$ 2 time the upper limit of normal
Treatment Description	¹⁸ F-DCFPyL whole body PET/CT scan administered at the following timepoints: 1) Prior to scheduled nephrectomy 2) After completion of systemic antiangiogenesis and/or immune-based therapy 3) When patient is refractory to treatment
Study Procedures	
 ¹⁸F-DCFPyL whole body PET/CT scan Review of relevant imaging and medical record information
Statistical Considerations	A total of 15 patients will be recruited into the clinical study. This is based on the feasibility and availability of suitable patients over the funding period with

	approximately five patients per year. With 15 patients, the mean of quantitative endpoints such as tumor size and SUV parameters will have standard error that is 0.258 times the sample standard deviation, and the width of a 95% confidence interval for the probability of binary qualitative endpoints such as objective response will be less than 0.253.
--	---

1.0 INTRODUCTION

Renal cell carcinoma (RCC) is the third most common genitourinary malignancy in the United States with ~64,000 new cases and ~14,000 deaths per year (Siegel 2017). Despite the increase in the number of treatment options, median overall survival for patients with metastatic RCC (mRCC) remains at less than 2 years (Heng 2013).

The purpose of this research is to build on previous success with using patient's own cells to predict their response to first line therapies for the treatment of multiple myeloma (MM). This research represents a transdisciplinary approach that leverages the recent development of a practical, functional, and adaptable *in vitro/ex vivo* model of RCC vascularization, coupled with novel prostate-specific-membrane antigen (PSMA)-based PET imaging of tumor neovasculature, to evaluate the model's ability to predict an individual patient's response to anti-angiogenic therapeutics.

2.0 RATIONALE

Recently, [name]'s Laboratory has shown in a retrospective study that harnessing the micro scale to retain critical multi-cellular signaling, e.g. stromal-cancer, allows the use of a patient's own cells to predict that patient's response to first line therapy, i.e. bortezomib, in multiple myeloma (MM) (Pak 2015). There are multiple cell types in the bone marrow microenvironment, including bone marrow stromal cells (BMSCs), macrophages, osteoclasts, and other immune cells, which secrete factors, e.g. cytokines, known to regulate signaling pathways that may contribute to chemotherapy resistance in MM (Asimakopoulos 2013, Hideshima 2007, Hope 2014, Kim 2012, Markovina 2010). Therefore, in the Pak (2015) study, [name]'s lab used a simple, yet novel, micro scale co-culture system to create a companion diagnostic (CDx) to measure the drug response of cancer cells taken from the patient (Fig. 1, top). We will work together with [name] and his lab to adapt and apply an analogous approach (Fig. 1, bottom) using a micro scale organotypic co-culture model (subsequently referred to as uVESSEL) to predict response to anti-angiogenic therapies in RCC.

[figure not shown]

Fig. 1 - Top - Patient specific co-culture system used to predict response to first-line therapy in MM (Pak 2015). Bottom - Analogous approach for RCC with endothelial cells as target (and readout) for response to anti-angiogenic drugs.

RCC is the third most common genitourinary malignancy in the United States with ~64,000 new cases and ~14,000 deaths per year (Siegel 2017). Clear cell RCC accounts for up to 85% of all RCCs and is different from MM in important ways. Clear cell RCC tumors are highly vascularized with blood vessels comprising approximately 25% of the tumor volume, increasing the supply of nutrients and driving tumor growth and metastasis. These tumor-associated blood vessels are enlarged, lack hierarchy, have a leaky endothelial layer, have abnormal disconnected sprouts, and have up-regulated soluble factor secretion when compared to their normal counterparts (Dudley 2012). Thus, endothelial cells and neovascularity are key components of the RCC tumor biology and, therefore, anti-angiogenic drugs have been the

preferred approach to treat RCC. Anti-angiogenic drugs are designed to target existing blood vessels and prevent the generation of new blood vessels in addition to normalizing the vessels within the tumor to improve the delivery of chemotherapeutics in a combination therapy (Hida 2016). Thus, while cancer cells were the therapeutic target in MM, endothelial cells are the therapeutic target in RCC (Fig. 1). Yet as decades of testing with Chemotherapy Sensitivity and Resistance Assays (CSRAs) attest (Editorial 2013) and recent American Society of Clinical Oncology (ASCO) guidelines confirm (Burstein 2011), examining the target cell in isolation is insufficient to predict patient response reliably. However, [name]'s recent MM work (Pak 2015), as well as work by Ramamoorthy (2015), has shown that inclusion of patient specific cancer-stroma interactions can enable accurate prediction of drug response. In this study, we will include the tumor milieus via incorporation of tissue explants in our micro scale RCC CDx (Fig. 1, bottom).

Despite increased clinical options, overall outcomes remain poor in RCC highlighting the need for predictive assays - Over the last decade, treatment options for mRCC have increased with the development of targeted agents that inhibit tumor angiogenesis. Unfortunately, median overall survival for mRCC patients remains less than 2 years (Heng 2013) and there remains an urgent need to improve treatment of mRCC patients. The first line agents pazopanib and sunitinib are multi-targeted small molecule, tyrosine kinase inhibitors (TKI) that inhibit a broad range of receptors for pro-angiogenic factors including VEGFR, PDGFR, and c-kit among others. These therapies are thought to act primarily or exclusively on tumor endothelial cells, decreasing tumor blood supply ([name] 2010). Axitinib and cabozantinib have similar (and also distinct) mechanisms of action, but clinically these agents are used as a second-line therapy only when primary agents fail. Importantly, wide variation in treatment responses to different agents has been demonstrated in clinical trials with anti-angiogenic therapies (Heng 2013). Currently, no biomarkers are available to predict which therapy will provide the best response to individual tumors and a "trial and error" approach is used to select initial treatments for mRCC patients. This standard paradigm is based on randomized clinical trial data demonstrating better clinical outcomes. The disadvantages of this empiric (and population-based) approach to selecting initial treatments in mRCC is also magnified by the rapid development of ten FDA approved therapies in ten years. This rapid expansion of new agents quickly outpaced the ability to evaluate these treatments in clinical trials. In 2017, clinicians and patients now have many choices for systemic treatment of mRCC, but desperately need tools for selecting the best treatments for individual patients. A better approach would be to test each patient with a CDx to determine which of the many available drugs is most appropriate for that patient, resulting in precision medicine for treatment of patients with mRCC.

As discussed above, the molecular pathogenesis of RCC is intrinsically linked to angiogenesis and the use of anti-angiogenic drugs. Our micro scale model will recapitulate patient vasculature and we need a method to measure vascularization *in vivo* in patients in order to evaluate the predictive value of our model. Current conventional imaging response criteria originally developed to assess response to chemotherapy using computed tomography (CT), such as RECIST1.1, are limited for determining treatment response to anti-angiogenesis agents (Ammari 2014). In order to monitor response in patients we can exploit the highly vascularized tumors in RCC, using a positron emission tomography (PET) radiotracer targeting the tumor neovasculature to reliably image RCC metastatic lesions. A new PET radiotracer for imaging angiogenesis targets the cell surface protein, prostate-specific membrane antigen (PSMA), which, despite the specificity implied by its name, is highly expressed on the tumor neovasculature of a number of solid tumors including a variety of RCC subtypes but most pronounced in clear cell RCC (Baccala 2007, Al-Ahmadie 2008). Recent studies by ourselves and others have reported

PSMA-based PET detection of metastatic RCC (Siva 2017, Gorin 2017, Rhee 2016, Rowe 2015 & 2016). The development of PET imaging compounds targeted to the vascular endothelium allows direct imaging of tumor neovasculature, avoiding the limitations of indirect methods such as traditional contrast enhanced imaging. Thus, PSMA PET imaging addresses a major unmet clinical need in metastatic RCC for a reliable non-invasive functional imaging method for metastatic tumor detection and response to therapy, especially for anti-angiogenesis treatments.

In addition to anti-angiogenesis agents, immunotherapy has also been shown to play an important role in the treatment of patients with metastatic RCC. Nivolumab is an anti-programmed cell death 1 (PD-1) monoclonal antibody that was approved by FDA in 2015 based on a phase III clinical trial that showed improvement in survival compared to the mTOR inhibitor everolimus in patients whose disease had developed resistance to anti-angiogenesis therapies (Motzer 2015). More recently, combination immunotherapy with nivolumab and ipilimumab, which is an anti-cytotoxic T-lymphocyte-associated protein 4 (CTLA-4) monoclonal antibody, demonstrated improvement in survival compared to sunitinib (Motzer 2018) and eventually became the preferred standard-of-care first-line treatment for patients with metastatic RCC. Finally, two additional trials that were published in March of 2019 showed that the combination of axitinib with anti-PD-1 immunotherapy (pembrolizumab and avelumab respectively) [Rini 2019; Motzer, 2019] showed superiority compared to sunitinib and are currently pending approval by FDA as first-line therapies for metastatic RCC. In this rapidly evolving field, it is unclear how the most recent studies will impact the care of these patients, however systemic therapy with anti-angiogenesis agents will continue to play an important role.

3.0 OBJECTIVES

3.1 Primary Objective: To evaluate response to systemic therapy, including anti-angiogenesis and/or immune-based therapies, via ¹⁸F-DCFPyL PSMA-based PET/CT in patients with metastatic renal cell carcinoma and to compare qualitatively with conventional imaging response criteria (RECIST 1.1) and other histopathological endpoints including isolation, enumeration and staining of Circulating Tumor Cells (CTC).

Response of systemic immune-based and/or anti-angiogenesis therapies will be quantified using PSMA-based PET imaging using a novel agent, ¹⁸F-DCFPyL, as a non-invasive imaging biomarker of tumor neovasculature to functionally monitor renal cell cancer neovasculature in patients undergoing systemic anti-angiogenesis therapy. PSMA PET will be compared with response to anti-angiogenesis therapy using conventional imaging computed tomography(CT)-based RECIST1.1 criteria (Eisenhauer 2009) as well as histopathological endpoints (tumor vascular density, immunohistochemical staining for PSMA and neovascularization (CD105, CD31). Whole body PSMA PET/CT scans will be obtained at baseline, following adjuvant anti-angiogenic therapy and when the patient becomes refractory to treatment.

The rationale and time points for obtaining PET scans is planned with respect to the typical natural history of metastatic RCC. This project will obtain information from tumors that are responding to anti-angiogenesis therapy and those resistant to treatment.

PET1 is obtained pre-surgically to establish the baseline tumor PET and CT characteristics prior to

surgical removal of the primary renal tumor and metastatic sites (e.g. LNs). Surgery technique is not altered for this study.

PET2A is obtained post-surgery and prior to start of first line standard-of-care (SOC) systemic therapy, either immune-based and/or anti-angiogenesis therapy. If the first line SOC systemic therapy is an immune-based therapy, a PSMA-based ¹⁸F-DCFPyL PET/CT will be obtained as PET2A and PET2B imaging time points, with potential PET3A and PET3B imaging as possible intended anti-angiogenesis therapy. The purpose of PET2 imaging is to establish a new baseline PET before first line SOC systemic therapy commences, given that post-surgical healing is a complex process that also includes angiogenesis and post-surgical inflammatory changes with potential changes in PET imaging. PET2 is necessary to characterize the existing metastatic tumors and any metastatic tumors which develop between PET1 and beginning systemic therapy. Clinical imaging with standard imaging is also obtained at this time as per standard care.

PET2B is obtained at 12-16 weeks from start of first-line SOC systemic therapy, either immune-based and/or anti-angiogenesis therapy (with associated SOC conventional diagnostic chest/abdomen/pelvis CT) to evaluate mRCC tumors response to treatment. This time point is chosen given that less than 10% of patients will have progressive disease on SOC conventional imaging at their initial evaluation.

PET3A and **PET3B** are obtained as follows, if the first line SOC systemic therapy did not include an anti-angiogenesis therapy and if this new systemic therapy includes an anti-angiogenesis therapy:

PET3A is obtained prior to start of additional systemic therapy including anti-angiogenesis therapy. The purpose of PET3A imaging is to establish a new baseline PET before this systemic therapy commences. PET3A is necessary to characterize the existing metastatic tumors and any metastatic tumors which develop between PET2B and start of this systemic therapy. Clinical imaging with standard imaging is also obtained at this time as per standard care.

PET3B is obtained at 12-16 weeks from start of this new systemic therapy including anti-angiogenesis therapy (with associated SOC conventional diagnostic chest/abdomen/pelvis CT) to evaluate mRCC tumors response to treatment.

PET4 is obtained at clinical progression per (RECIST 1.1) or 2 years following initial systemic therapy, whichever occurs first. In patients with progressive disease, PET imaging will be used to evaluate changes in index lesions. In recent review (NEJM 2017) of clinical trials for first line mRCC therapies, the median time to progression on therapy is less than one year (range 3.1-11 months), with median OS about 2 years (range 7.3- 29 months). (Krajewski 2014 and Choueiri 2017).

3.2 Secondary Objectives:

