If the first line SOC systemic therapy did not include an anti-angiogenesis therapy and if this second systemic therapy includes anti-angiogenesis therapy, an additional 4th and 5th PET imaging will be obtained as PET3A and PET3B. PET3A is obtained prior to start of additional systemic therapy including anti-angiogenesis therapy, to establish a new baseline PET before this systemic therapy commences, to characterize the existing metastatic tumors and any metastatic tumors which develop between PET2B and start of this systemic therapy. PET3B is obtained at 12-16 weeks from start of this second systemic therapy including anti-angiogenesis therapy (with associated SOC conventional diagnostic chest/abdomen/pelvis CT) to evaluate mRCC tumors response to treatment.

Following recovery from surgery the patients will initiate systemic therapy as per SOC. The patients will receive systemic therapy with an antiangiogenic agent as per first-line or later SOC therapy. There are currently 4 oral antiangiogenic agents approved by FDA for the treatment of patients with metastatic RCC (pazopanib, sunitinib, cabozantinib, axitinib) and patients on this study will receive one of those 4 agents as per physician's preference.

Study procedures will include a tissue analyses as well as the use of PET/CT imaging to monitor subject's clinical response to treatment. For tissue, immune cell and CTC analyses, investigators will be working with the UWCCC Biobank staff to acquire blood samples and tissue samples donated from the kidney with primary tumor, lymph nodes, and any other metastatic site from which tissue was collected.

Subjects will be asked to complete four to six research visits that will include the administration of a PSMA PET/CT exam. There will be an initial baseline ¹⁸F-DCFPyL PSMA PET/CT (PET1) prior to nephrectomy and SOC biopsy of metastatic sites as clinically indicated, followed by a second ¹⁸F-DCFPyL PSMA PET/CT (PET2A) prior to start of systemic anti-angiogenesis and/or immune-based therapy. A third on-treatment ¹⁸F-DCFPyL PSMA PET/CT (PET2B) will be performed at 12-16 weeks from start of systemic therapy (with associated SOC diagnostic chest/abdomen/pelvis CT). If system The fourth (or sixth if there is PET3A and PET3B) ¹⁸F-DCFPyL PSMA PET/CT (PET4) will be performed at the time of disease progression as determined by conventional imaging such as CT or MRI; or two years after initiation of therapy (whichever one comes first).

Blood and Tissue Collection

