Medical records will be reviewed to obtain medical history including physical exams, medications (all concomitant medications before and after each of the PET/CT scans, treatment medications for RCC), laboratory tests (metabolic chemistry, hematology, pathology), imaging results (all available CT, MRI, ultrasound, PET/CT) and information related to the diagnosing, treatment, or outcomes of the study subject's diagnosis, treatment and clinical follow-up up to two years from the time of initiation of systemic anti-angiogenesis therapy.

Remuneration

Subjects will receive \$50 per scan, for a total of up to \$300, as compensation for their participation in this study.

Withdrawal/Termination from Study

Reasons for withdrawal or termination

Enrolled patients will be removed from the study in the following circumstances:

- The patient does not complete the imaging examinations per study protocol
- The subject withdraws consent
- Exclusion criteria are discovered after registration but prior to the research examinations
- The PI or co-investigators determine it is within the best interest of the subject to remove them from the research.

Study Procedures Table

Study Procedures	Screening ¹	Baseline Prior to surgery	VISIT 2a and 2b Prior to and during 1 st systemic therapy	VISIT 3a and 3b Prior to and during 2 nd systemic therapy	VISIT 4 ²
Informed Consent ⁵	X				
Clinical History	X				
PET/CT Exam		X	X ⁴	X ⁴	X
Tissue Collection			X ³		

1. Screening visit may be completed on the same day as the baseline visit
2. To be done at the time of disease progression or within 2 years, whichever occurs first.
3. Tissue collection will occur post SOC surgery and will be coordinated with the UWCCC TSB.
4. PET/CT scan obtained prior to systemic therapy (immune-based and/or anti-angiogenesis therapy) and at 12-16 weeks into therapy
5. During the COVID-19 pandemic, consent procedures will be conducted by phone, when possible, to minimize face-to-face contact subjects have with the research team. An encrypted copy of the consent form will be mailed or emailed to subjects prior to the scheduled consent phone call.

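### The under-10% progression figure behind the PET2B timing is unsourced and hard to reconcile with the cited medians, and no rule says how early progressors enter the PSMA-PET response rate

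*Combined protocol and SAP*

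**What the plan says.** Section 3.1 fixes the first response assessment: "PET2B is obtained at 12-16 weeks from start of first-line SOC systemic therapy, either immune-based and/or anti-angiogenesis therapy". A conventional CT goes with it: "with associated SOC conventional diagnostic chest/abdomen/pelvis CT) to evaluate mRCC tumors response to treatment". The reason given for the timing is "This time point is chosen given that less than 10% of patients will have progressive disease on SOC conventional imaging at their initial evaluation". Section 5.0 repeats that reason, and neither place cites a source or shows a derivation.

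The PET4 paragraph of 3.1 says of first-line trials that "the median time to progression on therapy is less than one year (range 3.1-11 months"). It sets the trigger for the last scan: "PET4 is obtained at clinical progression per (RECIST 1.1) or 2 years following initial systemic therapy, whichever occurs first". It adds: "In patients with progressive disease, PET imaging will be used to evaluate changes in index lesions".

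Section 5.0 states: "Subjects will be asked to complete four to six research visits that will include the administration of a PSMA PET/CT exam". Its withdrawal subsection lists, among the reasons for removing an enrolled patient from the study: "The patient does not complete the imaging examinations per study protocol".

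Section 10.2 makes PSMA-PET response the primary endpoint, to be summarised as a rate with a confidence interval. It gives no rule for a patient without a PET2B reading.

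**The concern.** Two things do not fit together. The first is the premise. If medians across trials run from 3.1 to 11 months, then 12-16 weeks is late enough that more than a tenth of patients could well have progressed by then.

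The second matters more for the analysis. Progression is the trigger for PET4, and a CT that can show progression is paired with PET2B. A patient whose CT at that visit shows progression meets both triggers at once. A patient who progresses sooner meets the PET4 trigger before PET2B is due. The plan does not say whether both scans are done, whether one serves as both, or which gives the response reading. The same gap applies to PET3B.

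The patients affected are selectively those who fail early. If the withdrawal rule takes them out, the PSMA-PET response rate rises for a reason unrelated to the tracer or the therapy. Section 3.2.2 also uses PET response as the dependent variable in the uVESSEL logistic model, so losing non-responders would weaken that analysis too.

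**Working it through.** **Inputs.** From the documents: under 10% progressed (3.1 and 5.0); PET2B at 12-16 weeks (3.1); medians m of 3.1 to 11 months (3.1); n = 15 (10.1). Assumed, because the documents give no shape for the progression-time distribution: a Weibull with shape k, where k = 1 is a constant hazard and k > 1 a rising one.

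**Reproducing the stated figure.** Not possible, because no derivation is given. It can only be tested against the cited medians.

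**Units.** 12 weeks = 12 × 7 / 30.4375 = 2.76 months; 16 weeks = 3.68 months.

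**Without any distribution.** Week 16 (3.68 months) lies beyond a 3.1-month median, so at least 50% have progressed by then. Under 10% is impossible at that point.

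**With the assumed shape.** F(t) = 1 − 0.5^((t/m)^k). For m = 11 and k = 1: 1 − 0.5^(2.76/11) = 16.0% and 1 − 0.5^(3.68/11) = 20.7%. Other values:

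| Median (months) | k | Week 12 | Week 16 |
|---|---|---|---|
| 11 | 1 | 16.0% | 20.7% |
| 11 | 1.25 | 11.6% | 16.2% |
| 11 | 1.5 | 8.3% | 12.6% |
| 11 | 2 | 4.3% | 7.5% |
| 3.1 | 1 | 46.0% | 56.1% |
| 3.1 | 2 | 42.3% | 62.3% |

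**What under 10% requires.** With a constant hazard, m > t × ln 2 / (−ln 0.9): 18.2 months for week 12 and 24.2 months for week 16, both outside the cited range. With m = 11, the shape must satisfy k ≥ ln(−ln 0.9 / ln 2) / ln(t/m): 1.36 for week 12 and 1.72 for week 16.

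**Does the rule gap depend on this?** No. Even at a true rate of 10%, the chance that at least one of 15 has progressed by PET2B is 1 − 0.9^15 = 79%. If only 10 reached that visit (an assumption for illustration), it is 1 − 0.9^10 = 65%.

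**Reading the rules together.** The four-visit minimum in 5.0 is PET1, PET2A, PET2B and PET4. An early progressor with a single on-treatment scan has three. The withdrawal subsection then offers a literal ground for removal.

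**Effect on the rate (illustration; 5 responders of 15 assumed).** All kept: 5/15 = 33%. One early progressor removed: 5/14 = 36%. Three removed: 5/12 = 42%.

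**The case against.** The case on the other side is substantial, and much of it stands.

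- A reader might infer that the protocol's own medians contradict the under-10% figure. They do so without further assumptions only where the median falls before the scan, as at 3.1 months and week 16. At 11 months a moderately rising hazard gives under 10%, and such a shape is plausible when progression is detected only at scheduled scans. The initial evaluation is also not dated on its own: at 11 months with a constant hazard, an assumed 6-week evaluation would give 8.3%. However, 3.1 ties the statement to the 12-16 week visit.
- A reader might take 46-56%, or 6.9 to 8.4 of 15 patients, as the expected loss. The range is across trials, and nothing places this untreated surgical cohort at its low end. Nor need all 15 reach PET2B: 5.0 gives locally advanced patients no PET2A until metastases appear.
- A reader might infer that the response reading will be lost. Often it need not be. A patient whose progression shows on the paired CT is already at the PET2B visit, and an earlier progressor has a PET4 scan that can be read against PET2A. What is missing is a statement that such a scan counts.
- A reader might infer that the RECIST rate is inflated as well. RECIST response comes from standard-of-care CT and does not depend on PET2B being done.
- Removal from the study need not mean exclusion from analysis, and 10.2 describes the analysis as exploratory. Both are true. But 10.2 does not say that removed patients stay in the denominator, and a descriptive study still reports the rate.

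**Conclusion.** The point holds in limited form and is worth correcting. The under-10% basis for PET2B is unsourced. It cannot hold at week 16 for a 3.1-month median, and at 11 months it holds only if the hazard rises enough; a constant hazard gives 16-21%. The documents do not support calling it contradicted across the whole range.

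The firmer finding is the missing rule. No text says which scan gives the response reading when progression occurs at or before PET2B or PET3B, and the withdrawal rule, read literally, can remove early failures from the primary PSMA-PET rate. At least one such patient is likely even on the plan's own premise: up to 79% at a 10% rate if all 15 reach PET2B, and less if fewer do. The shift from 33% to 42% is an illustration that assumes three removals, not a forecast. The upward bias is a risk that depends on how the rules are applied, not a certainty.

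**What to change.** 1. Give a source for the under-10% statement in 3.1 and 5.0, or reconcile it with the medians cited in the PET4 paragraph. Reconcile 3.1, the visit description in 5.0 and the withdrawal subsection on PET2B/PET3B versus PET4 when progression is early. Scan timing is for the sponsor; none is proposed here.
2. State in 10.2 that an on-treatment scan obtained at progression, on or before the PET2B or PET3B visit, is analysed against its pre-treatment baseline (PET2A or PET3A) as the response reading as well as the progression reading.
3. State in 10.2 that removal under the withdrawal subsection does not take a patient who started systemic therapy out of the response-rate denominator. An early progressor with no on-treatment PET scan is a RECIST non-responder. For PSMA-PET, that patient stays in the denominator as not evaluable and is counted as not a responder, with a sensitivity analysis that leaves such patients out (5/15 against 5/12 in the illustration). The same patient is left out of the PET-versus-RECIST agreement table, because filling a missing PET result from RECIST would build in agreement between the two methods being compared.

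The cost is a few sentences in 3.1, 5.0 and 10.2, with no extra scans. The reported response rate may be slightly lower.
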